### 9.3.4 Events of Special Interest

Specific AEs, or groups of AEs, will be followed as part of standard safety monitoring activities by the Sponsor. These events (regardless of seriousness) will be reported to the Sponsor within 24 hours of awareness following the procedure described above for SAEs (Section 9.3.3) and will require enhanced data collection. **All Events of Special Interest will be submitted without a serious criterion selected if no other serious criterion is met.**

#### 9.3.4.1 Major Hemorrhage

Major hemorrhage is defined as any of the following:

- Any treatment-emergent hemorrhagic adverse events of Grade 3 or higher\*.
- Any treatment-emergent serious adverse events of bleeding of any grade
- Any treatment-emergent central nervous system hemorrhage/hematoma of any grade

\*All hemorrhagic events requiring transfusion of red blood cells should be reported as grade 3 or higher AE per CTCAE.

Events meeting the definition of major hemorrhage will be captured as an event of special interest according to Section 9.3.4 above.

### 9.3.5 Pregnancy

Before study enrollment, subjects must agree to take appropriate measures to avoid pregnancy. However, should a pregnancy occur (including female partners of male subjects), consent to provide follow-up information regarding the outcome of the pregnancy and the health of the infant until 30 days old will be requested.

A female subject must immediately inform the investigator if the subject becomes pregnant from the time of consent to 30 days after the last dose of study drug or a male subject must immediately inform the investigator if the subject's partner becomes pregnant from the time of consent to 3 months after the last dose of study drug. Any female subjects receiving PCI-32765 capsules who become pregnant must immediately discontinue the use of study drug. The investigator should counsel the subject, discussing any risks of continuing the pregnancy and any possible effects on the fetus.

Although pregnancy itself is not regarded as an AE, the outcome will need to be documented. Report any pregnancy that occurs in a subject or subject's partner from the time of consent to 30 days after the last dose of study drug. Record any occurrence of pregnancy on the Pregnancy Report Form Part I and email or fax to Pharmacyclics Drug Safety, or designee, within 24 hours of learning of the event. The pregnant female will be followed for outcome, which is defined as elective termination of the pregnancy, miscarriage, or delivery of the fetus. For pregnancies with an outcome of live birth, the newborn infant will be followed until 30 days old by completing the Pregnancy Report Form Part II. Any congenital anomaly/birth defect noted in the infant must be reported as a SAE.

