--	--

	
stomach or small bowel, or complete bowel obstruction.
 
28. History of prior malignancy, with the exception of the following:
 
 
a. Malignancy treated with curative intent and with no known active disease present for more than 3 years prior to screening and felt to be at low risk for recurrence by treating physician;
 
b. Adequately treated non-melanoma skin cancer or lentigo maligna without current evidence of disease; or
 
c. Adequately treated breast or cervical carcinoma in situ without current evidence of disease.
 
 
29. Peripheral neuropathy Grade <math>\geq 2</math> on clinical examination within 14 days prior to enrollment.
 
30. Uncontrolled diabetes mellitus.
 
31. Currently active systemic fungal, bacterial, viral, or other infection not controlled (defined as exhibiting ongoing signs/symptoms related to the infection and without improvement, despite appropriate antibiotics or other treatment).
 
32. Use of antibiotics for treatment of infection within 7 days prior to first dose of study drug.
 
33. Known history of infection with human immunodeficiency virus (HIV) or history of active infection with hepatitis C virus (HCV) or hepatitis B virus (HBV) or any uncontrolled active systemic infection.
 
34. History of stroke or intracranial hemorrhage within 6 months prior to the first dose of study drug.
 
39. Requires anticoagulation with warfarin or equivalent vitamin K antagonists (eg, phenprocoumon).
 
40. Requires treatment with strong CYP3A4/5 inhibitors (see Appendix 2)
 
Ethical/Other:
 
35. Subject is pregnant or breastfeeding.
 
36. Will not agree to use highly effective contraception (eg, condoms, implants, injectables, combined oral contraceptives, some intrauterine devices [IUDs], sexual abstinence, or sterilized partner) during the study and for 30 days after the last dose of study drug. (Note: applies to women of child-bearing potential or men with female partners of child-bearing potential only.)
 
37. Any other life-threatening illness, medical condition, or organ system dysfunction that, in the investigator’s opinion, could compromise the subject’s safety, or put the study outcomes at undue risk.
 
38. Any medical or psychiatric condition that, in opinion of investigator, could interfere with the subject’s ability to give informed consent, compliance, or treatment.

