39. Requires anticoagulation with warfarin or a vitamin K antagonist (eg, phenprocoumon).
40. Requires treatment with strong CYP3A4/5 inhibitors (see [Appendix 2](#)).

*Ethical/Other*

35. Subject is pregnant or breastfeeding.
36. Will not agree to use highly effective contraception (eg, condoms, implants, injectables, combined oral contraceptives, some intrauterine devices [IUDs], sexual abstinence, or sterilized partner) during the study and for 30 days after the last dose of study drug. (Note: applies to women of childbearing potential or men with female partners of childbearing potential only.)
37. Any other life-threatening illness, medical condition or organ system dysfunction that, in the investigator's opinion, could compromise the subject's safety, or put the study outcomes at undue risk.
38. Any medical or psychiatric condition that, in opinion of investigator, could interfere with the subject's ability to give informed consent, compliance, or treatment.

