### **6.8.2 Reproductive Toxicity**

Reproductive toxicity studies have not been conducted with PCI-32765. Therefore, women of childbearing potential, who are sexually active, must use highly effective contraception (as listed in [Section 5.2](#)) during the study and for 30 days after the last dose of study drug. Men who are sexually active, must use highly effective contraception during the study and for 90 days (3 months) after the last dose of PCI-32765. Subjects should promptly notify the investigator if they, or their partner, become pregnant during this period. If a female subject becomes pregnant during the treatment period, she must discontinue study drug immediately. Pregnancy in a female subject or a male subject's partner must be reported in the same manner as an SAE ([Section 9.3.5](#)).

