#### 9.3.1 Adverse Event Reporting Period

The AE reporting period for this study begins with the first dose of study drug and ends 30 days following the last dose of study drug. SAEs occurring after 30 days following the last dose of study drug should also be reported to the Sponsor if considered related to study drug. If an SAE is present at the Safety Follow-up visit, the SAE (and associated AEs and concomitant medications) should be followed to resolution or until the investigator assesses the subject as stable or the subject is lost to follow-up or withdraws consent. Resolution/stable means the subject has returned to baseline state of health or the investigator does not expect any further improvement or worsening of the event.

If a death occurs within 30 days after the last dose of study drug (even if the Safety Follow-up visit has already occurred), the death must be reported to the Sponsor as an SAE.

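### Section 9.3.5 makes men notify partner pregnancies for 3 months after the last dose, but its reporting sentence stops at 30 days

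*Protocol*

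**What the plan says.** Section 9.3.5 of the protocol handles pregnancy in three steps.

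- **Notification to the site.** A female subject must inform the investigator of a pregnancy up to 30 days after the last dose. A male subject must do so if his partner "becomes pregnant from the time of consent to 3 months after the last dose of study drug".
- **Reporting by the site.** The next paragraph tells the site which pregnancies to report. It names both the subject and the subject's "partner from the time of consent to 30 days after the last dose of study drug. Record any occurrence of pregnancy".
- **Form and follow-up.** The instruction then continues: "Record any occurrence of pregnancy on the Pregnancy Report Form Part I and email or fax to" Drug Safety within 24 hours. The pregnancy is followed to outcome, and a live-born infant to 30 days of age.

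Three other places bear on the same windows.

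- **Section 6.8.2** states that reproductive toxicity studies have not been done. Sexually active men "must use highly effective contraception during the study and for 90 days (3 months) after the last dose of PCI-32765", and subjects are asked to tell the investigator promptly of a pregnancy in that period. Pregnancy in a subject or partner "must be reported in the same manner as an SAE", with a cross-reference to Section 9.3.5.
- **Exclusion criterion 36** concerns willingness to use contraception. Section 5.2 sets the period as "during the study and for 30 days after the last dose of study drug. (Note: applies to women of childbearing potential or men" with partners of childbearing potential. The Synopsis version has the same limit: "for 30 days after the last dose of study drug. (Note: applies to women of child-bearing potential or men".
- **Section 9.3.1** ends routine adverse event reporting at 30 days and adds: "SAEs occurring after 30 days following the last dose of study drug should also be reported to the Sponsor if considered related".

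**The concern.** The 30-day reporting limit equals the female notification window, but it is applied to partners as well, for whom the same section uses 3 months. A site that follows the reporting sentence literally can receive a partner pregnancy on, say, day 60 and conclude that it falls outside the reporting period. Another site, relying on the next sentence or on Section 6.8.2, would report it. Both could claim to have followed the protocol.

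What is at stake is systematic capture and outcome follow-up of pregnancies in a period the protocol itself treats as one of risk for men, for a drug it says has had no reproductive toxicity studies. A congenital anomaly that becomes known must be reported as an SAE in its own right. A miscarriage or elective termination has no such separate route in Section 9.3.5, and an anomaly is found reliably only if the pregnancy is followed.

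Criterion 36 carries the mismatch into eligibility: a man can pass the screen having agreed to one third of the post-dose contraception that Section 6.8.2 demands.

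**Working it through.** This is mainly a comparison of text; no power, alpha or sample-size figure is involved, and the plan states no figure to reproduce.

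**Windows side by side**

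| Provision | Whom it covers | End of window after last dose |
|---|---|---|
| 9.3.5, notification | Female subject | 30 days |
| 9.3.5, notification | Male subject's partner | 3 months |
| 9.3.5, reporting sentence | Subject or partner | 30 days |
| 6.8.2, contraception | Women | 30 days |
| 6.8.2, contraception | Men | 90 days (3 months) |
| Criterion 36, agreement to contraception | Women and men | 30 days |

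The female rows agree throughout. The male rows do not: the reporting sentence and criterion 36 use 30 days where the other two provisions use 3 months or 90 days.

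**Size of the gap.** Section 6.8.2 equates 3 months with 90 days.

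- Days outside the reporting sentence: 90 − 30 = 60, that is days 31 to 90.
- Share of the post-dose notification window: 60/90 = 67%.

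**Share of treatment plus 90 days.** With 28-day cycles, the share is 60/(28 × cycles + 90). The number of cycles is an assumption, and the time from consent to first dose is left out, which would lower the shares slightly.

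- 1 cycle: 60/(28 + 90) = 60/118 = 51%
- 6 cycles: 60/(168 + 90) = 60/258 = 23%
- 12 cycles: 60/(336 + 90) = 60/426 = 14%

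These are shares of calendar time. They are not risks, and they do not estimate missed reports.

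**Does other text close the gap?**

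1. The sentence telling sites to record any pregnancy has no time limit. It comes directly after the 30-day sentence, so it can equally be read as the procedure for the pregnancies just defined.
2. Section 6.8.2 requires SAE-style reporting of partner pregnancies right after the 90-day rule, which supports the longer window. It sends the reader to Section 9.3.5 for the detail, and that is where the conflict lies.
3. If a site applies the SAE period of Section 9.3.1, it finds a 30-day limit again, with later events reported only if considered related.

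None of these overrides an explicit 30-day limit that names partners.

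**The case against.** The strongest reply is that the gap is one of wording and that loss of data is not shown. Section 9.3.5 surrounds the 30-day sentence with instructions that carry no time limit: consent for follow-up is sought if a pregnancy occurs, including in partners; any pregnancy is recorded and sent within 24 hours of learning of it; and the pregnant woman is followed for outcome. Section 6.8.2, read in order, covers the 90 days. Nothing forbids a site from reporting a day-60 case. This stands in part: some sites, perhaps most, would report. It does not remove the conflict, because the only sentence in Section 9.3.5 that defines which pregnancies to report limits partners to 30 days.

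Four further points deserve credit.

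- Section 9.3.5 says pregnancy itself is not an adverse event, and Section 6.8.2 borrows only the manner of SAE reporting, so the relatedness condition in Section 9.3.1 may not apply. The conclusion does not need Section 9.3.1.
- The percentages by number of cycles rest on assumed treatment lengths. Only the 60 of 90 days comes from the documents.
- Criterion 36 is a screen of willingness. An enrolled man is still bound by the 90-day rule in Section 6.8.2, so the practical effect of that mismatch is limited. The consent form wording is not available to check.
- The matter is an internal inconsistency in safety reporting. It does not touch the SAP, the primary endpoint, sample size or error rates.

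**Conclusion.** The concern holds. The current text of Section 9.3.5 gives partner pregnancies a 3-month notification window and a 30-day reporting window, and no other provision settles which governs. The uncertain interval is days 31 to 90 after the last dose: 60 days, or two thirds of the male post-dose window, taking 3 months as 90 days as Section 6.8.2 does. Section 6.8.2 indicates that the longer window is the intended one for men. Criterion 36 has the same 30 versus 90 day mismatch for contraception.

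The number of affected pregnancies cannot be derived from the documents and is probably small in this population. The correction is worth making because the rule is wrong as written, the drug's reproductive toxicity has not been studied according to the protocol, and the change costs almost nothing.

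**What to change.** **Section 9.3.5.** Reword the reporting sentence so that sites report any pregnancy in a female subject from consent to 30 days after the last dose, and any pregnancy in a male subject's partner from consent to 3 months (90 days) after the last dose, with the same form, 24-hour timeline and outcome follow-up for both.

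**Exclusion criterion 36 (Section 5.2 and Synopsis).** Set the post-dose contraception period to 30 days for women and 90 days for men, matching Section 6.8.2.

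**Cost.** One sentence and one phrase (the latter in two places). No visits or tests are added, since men must already notify the site through 3 months. If enrolment has closed, the criterion 36 edit has little practical effect. The Section 9.3.5 change still matters for any man on treatment or within 3 months of his last dose, and could go to sites as a clarification until the amendment is in place.

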### **9.3.6 Other Malignancies**

In addition to all routine AE reporting, all new malignant tumors including solid tumors, skin malignancies and hematologic malignancies are to be reported for the duration of study including the post-progression follow-up period for overall survival.

## **9.4 Reporting of Serious Adverse Events by Sponsor**

Regulatory Authorities, Institutional Review Boards/Independent Ethics Committees (IRBs/IECs), and Principal Investigators will be notified of SAEs in accordance with applicable requirements (eg, GCPs, ICH guidelines, national regulations, and local requirements).

## **10.0 STUDY ADMINISTRATION AND INVESTIGATOR OBLIGATIONS**

Pharmacyclics retains the right to terminate the study and remove all study materials from a study site at any time. Specific circumstances that may precipitate such termination are:

- Unsatisfactory subject enrollment with regard to quality or quantity (eg, < 12 subjects enrolled within 12 months of starting the study).
- Significant or numerous deviations from study protocol requirements, such as failures to perform required evaluations on subjects and maintain adequate study records.
- Inaccurate, incomplete and/or late data recording on a recurrent basis.
- The incidence and/or severity of AEs in this or other studies indicate a potential health hazard caused by the study treatment.

### **10.1 Institutional Review Board and Independent Ethics Committee**

The investigator will submit this protocol, the ICF, IB, and any other relevant supporting information (eg, all advertising materials or materials given to the subject during the study) to the appropriate IRB/IEC for review and approval before study initiation. Amendments to the protocol and ICF must also be approved by the IRB/IEC before the implementation of changes in this study.

The investigator is responsible for providing the IRB/IEC with any required information before or during the study, such as SAE expedited reports or study progress reports.

The IRB/IEC must comply with current US regulations (§21 CFR 56) as well as country-specific national regulations and/or local laws.

The following documents must be provided to Pharmacyclics or its authorized representative, before entering subjects in this study: (1) a copy of the IRB/IEC letter that grants formal approval and (2) a copy of the IRB/IEC-approved ICF.

### **10.2 Informed Consent**

The ICF and process must comply with the United States regulations (§ 21 CFR Part 50) as well as country specific national regulations and/or local laws. The ICF will document the study-specific information the investigator or his/her designee provides to the subject and the subject's agreement to participate.

The investigator, or designee (designee must be listed on the Delegation of Authority log), must explain in terms understandable to the subject the purpose and nature of the study, the study procedures, anticipated benefits, potential risks, the possible adverse effects, and any discomfort participation in the study may entail. Each subject must provide a signed and dated ICF before any study-related (nonstandard of care) activities are performed (such as screening).

The original and any amended signed and dated consent forms must remain in each subject's study file at the study site and be available for verification by study monitors at any time.

A copy of each signed consent form must be given to the subject at the time that it is signed by the subject.

### **10.3 Protected Subject Health Information Authorization**

Information on maintaining subject confidentiality in accordance to individual local and national subject privacy regulations must be provided to each subject as part of the informed consent process (refer to Section 10.2), either as part of the ICF or as a separate signed document (for example, in the US, a site-specific Health Insurance Portability and Accountability Act consent may be used). The investigator or designee must explain to each subject that for the evaluation of study results, the subject's protected health information obtained during the study may be shared with Pharmacyclics and its designees, regulatory agencies, and IRBs/IECs.

As the study sponsor, Pharmacyclics will not use the subject's protected health information or

disclose it to a third party without applicable subject authorization. It is the investigator's or designee's responsibility to obtain written permission to use protected health information from each subject. If a subject withdraws permission to use protected health information, it is the investigator's responsibility to obtain the withdrawal request in writing from the subject and to ensure that no further data will be collected from the subject. Any data collected on the subject before withdrawal will be used in the analysis of study results.

During the review of source documents by the monitors or auditors, the confidentiality of the subject will be respected with strict adherence to professional standards and regulations.

#### **10.4 Subject Screening Log**

The investigator must keep a record that lists all subjects considered for enrollment (including those who did not undergo screening) in the study. For those subjects subsequently excluded from enrollment, record the reason(s) for exclusion.

#### **10.5 Source Documentation Requirements**

The investigator/study staff must maintain adequate and accurate records to enable the conduct of the study to be fully documented and the study data to be subsequently verified. Source documentation for this study will include, but not be limited to, worksheets, hospital and/or clinic or office records documenting subject visits including study and other treatments or procedures, medical history and PE information, laboratory and special assessments results, pharmacy records, drug accountability records, and medical consultations (as applicable).

#### **10.6 Case Report Forms**

Electronic case report forms will be used to collect the clinical study data and must be completed for each enrolled subject with all required study data accurately recorded such that the information matches the data contained in medical records (eg, physicians' notes, nurses' notes, clinic charts and other study-specific source documents). Authorized study site personnel (ie, listed on the Delegation of Authority form) will complete eCRFs designed for this study according to the completion guidelines that will be provided. The investigator will ensure that the eCRFs are accurate, complete, legible, and completed as soon as reasonably possible. At all times, the investigator has final responsibility for the accuracy and authenticity of all clinical data.

The eCRFs exist within an electronic data capture (EDC) system with controlled access managed by Pharmacyclics or its authorized representative for this study. Study staff will be appropriately trained in the use of eCRFs and application of electronic signatures before the start of the study and before being given access to the EDC system. Original data and any changes of data will be recorded using the EDC system, with all changes tracked by the system and recorded in an electronic audit trail. The investigator attests that the information contained in the eCRFs is true by providing electronic signature within the EDC system. After database lock, the

investigator will receive a copy of the subject data (eg, paper, CD-ROM or other appropriate media) for archiving at the study site.

